#### 6.4.3.3 Eye comfort index

It is a questionnaire designed to measure the irritation of the ocular surface with Rasch analysis to produce estimates on a linear scale of intervals (ratings: 0-100). Similar to the index for ocular surface diseases, the ocular comfort index (ICO) evaluates symptoms. The ICO contains 8 items (one positive and eight negative) that focus on the discomfort associated with alterations of the ocular

Version: 1.0

surface. Each of these questions has two parts, which inquire separately the frequency and severity of the symptoms. [43] See annex 13.1 Eye comfort index.

The evaluator will deliver the questionnaire to the subject and allow the subject to answer it calmly without any pressure and / or coercion, will only assist him if he has difficulty understanding any of the questions.

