#### 6.3 Intervention

# 6.3.1 Managed treatments

# 6.3.1.1 Treatment under study

#### PRO-167

- o Active ingredients: Dexpanthenol 5%
- o Pharmaceutical form: Ophthalmic gel.
- o Prepared by: Sophia Laboratories A.S. of V.C.
- Posology: a strip approximately 1 cm long, 4 times a day during the waking period, in the bottom of the right eye sac.
- Description of the formulation: transparent gel, free of visible particles.
- o Description of the packaging: sterile multi-dose tube, low density polyethylene polyethylene and aluminum with high density polyethylene lid.

Table 3. Quali-quantitative formulation of PRO-167

Type of agent	Amount mg/mL	Function
Dexpanthenol	50.0	Active principle (lubricant)
Boric acid	2.00	Active principle
Sodium Borate decahydrate	without showing	additive
Polysorbate 80	without showing	additive
Sorbitol	without showing	additive
Potassium chloride	without showing	additive
Sodium chloride	without showing	additive
Magnesium Chloride hexahydrate	without showing	additive
Water for the preparation of injectables c.b.p.	1.00	Vehicle

Quali-quantitative formulation of the product under investigation PRO-167. The concentration of the active principles is shown, as well as the substances that act as a buffer additive.

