#### 6.4.1.2 Primary outcome variables of tolerability

- Burning
- Foreign body sensation
- Itching
- Eye comfort index

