#### Índice de confort ocular

5	en la seman	a pasada, ¿qi	ue tan seguido	sus ojos se sin	tieron aaolori	208 ?	
	Nunca						Siempre
	0	1	2	3	4	5	6
	Cuando sus	aias sa santí	an adoloridos	por lo general,	i quá tan into	nca ora la conc	ación?
	Cualiuo sus	ojos se senti	an uuolonuos ,	por lo general,	cque tan inte	iisa era ia seris	acions
	No lo he sentido						Severo
	0	1	2	3	4	5	6
6	En la seman	a pasada, ¿qı	ué tan seguido	sus ojos sintie	ron comezón ?	1	
	Nunca						Siempre
	0	1	2	3	4	5	6
	Cuando sus	ojos sentían	comezón , por	lo general, ¿qu	é tan intensa e	era la sensació	า?
	No lo he sentido						Severo
	0	1	2	3	4	5	6

Índice de confort ocular, traducido del Ocular Comfort Index disponible en: http://iovs.arvohournals.org Hoja 2 de 2

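### The eye comfort index, a primary tolerability variable, is described with an item count that does not match the annexed form, has no stated scoring rule, and asks about both eyes when only the right is treated

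*Combined protocol and SAP*

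**What the plan says.** Section 6.4.1.2 lists the eye comfort index under "Primary outcome variables of tolerability", beside burning, foreign body sensation and itching.

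Section 6.4.3.3 gives the content of the index: "The ICO contains 8 items (one positive and eight negative"). It adds that "Each of these questions has two parts, which inquire separately the frequency and severity of the symptoms", that the questionnaire was designed "with Rasch analysis to produce estimates on a linear scale of intervals (ratings: 0-100"), and then directs the reader to the form: "See annex 13.1 Eye comfort index".

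Annex 13.1 is a two-sheet Spanish form, "traducido del Ocular Comfort Index". It has six numbered items (dry, gritty, stinging, tired, sore, itchy), each with a frequency part and an intensity part answered 0 to 6. It shows no total, scoring key or conversion. Table 4 in section 6.4.3 gives the unit as points and the type as discrete, with no range.

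Sections 6.3.1.1 and 6.3.1.2 place each product "in the bottom of the right eye sac". Section 6.6.1 says that each subject contributes one eye to the analysis. Section 8.3.1 concludes that the product is safe and tolerable when no primary outcome differs from the comparator.

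**The concern.** There are two separate faults.

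**Item description and scoring.** The text gives a count that disagrees with its own breakdown, and neither figure matches the form. It names a positive item that the form lacks, and a 0-100 score with no route to it. An analyst working from the protocol alone would have to invent the scoring of a primary variable.

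**Which eye.** Every item refers to the subject's eyes in the plural and leaves no place to answer for one eye. The left eye receives no study product, so its comfort says nothing about how the product is tolerated. If its symptoms enter the answers, a real difference between arms could look smaller. The decision rule in section 8.3.1 treats absence of a difference as success, so any such dilution would favour the conclusion that PRO-167 is tolerable. Once the forms are filled in, the eye that the subject had in mind cannot be recovered.

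**Working it through.** **Inputs.** Item count and breakdown: section 6.4.3.3. Items, parts and answer range: annex 13.1. Treated eye: sections 6.3.1.1 and 6.3.1.2. Group size of 12 and alpha of 0.05: sections 6.6.1 and 8.3.1.

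**Step 1: the stated count.** The breakdown gives 1 + 8 = 9, against a stated 8. The plan's own figure is not reproduced.

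**Step 2: the form.** The numbered items run 1 to 4 on the first sheet and 5 to 6 on the second. The sheets are marked 1 of 2 and 2 of 2 and the numbering has no gap, so the form appears complete. The count is 6 items, none positive. Adding the unscored worked example about redness would make only 7.

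**Step 3: raw range.** Maximum = items × parts × top answer.

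| Items | Source of the count | Answers | Raw maximum |
|---|---|---|---|
| 6 | annex 13.1 | 12 | 6 × 2 × 6 = 72 |
| 8 | stated total | 16 | 8 × 2 × 6 = 96 |
| 9 | stated breakdown | 18 | 9 × 2 × 6 = 108 |

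No version yields 0-100 as a plain sum. A conversion is needed, and none appears in section 6.4.3.3, Table 4, section 8.3.1 or the annex. The reference number cited in section 6.4.3.3 leads to an entry in section 11 that carries no details.

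**Step 4: what depends on the scoring rule.** Multiplying the raw total by a constant leaves the Mann-Whitney and Wilcoxon results unchanged. A non-linear conversion that rises with the raw total keeps the order of subjects at one visit, but can change the ranking of within-subject changes. Reversing an item changes the order itself. Suppose subject A answers 6 and 6 on itching and 0 elsewhere (raw 12), and subject B answers 3 and 3 on dryness and 0 elsewhere (raw 6). With itching reversed, A scores 0 and B scores 6 + 12 = 18.

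**Step 5: the untreated eye.** The documents give no standard deviation, expected difference or information on how subjects combine two eyes, so the dilution cannot be estimated. Its possible range can be shown under assumptions: normal approximation, two-sided alpha 0.05, 12 per group, SD unchanged. Power ≈ Φ(d√(12/2) − 1.96), where d is the true difference in SD units. At one end, subjects report an irritated treated eye in full and d is unchanged. At the other, they average a treated and an untreated eye and d is halved.

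| True d | Power, reported in full | Power, halved |
|---|---|---|
| 0.5 | 0.23 | 0.09 |
| 1.0 | 0.69 | 0.23 |
| 1.25 | 0.87 | 0.33 |

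For d = 1.0: √6 = 2.449, and Φ(0.489) = 0.69; halved, Φ(1.225 − 1.96) = Φ(−0.735) = 0.23. The halving is an assumption, not a finding.

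**The case against.** **The score.** Section 6.4.3.3 attributes the 0-100 scale to Rasch analysis, not to a raw sum, and a 0-72 raw range does not exclude a Rasch conversion to 0-100. This stands. A reader might infer that the described scale is impossible for this form. The documents show only that no conversion is supplied, and that the positive item does not exist on the form.

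**The consequences of the wrong count.** A reader might also infer that scores would be capped below 100 because the sum would be divided by a maximum for eight or nine items, or that an analyst would reverse an item. The documents contain no instruction to sum and divide, and none to reverse. These are possible errors, not planned ones, and no effect on a result is shown.

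**Dilution.** It is tempting to say that the both-eyes wording pulls the arms together. That assumes subjects average their eyes. The items ask how often and how strongly a sensation was felt, and a subject with one irritated eye may report it in full. Subjects are also ophthalmologically healthy at entry, so the left eye may add little. Only the possibility of dilution stands.

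**Other measures.** Tolerability does not rest on this index alone. Section 6.4.3.9 records burning, foreign body sensation and itching by direct questioning and in the diary after each application, and section 8.3.1 requires no difference in every primary variable. This mitigation is real but partial. The direct questions do not name an eye either, and dryness, tiredness and soreness appear only in the index.

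**Conclusion.** The concern holds in a limited form.

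The mismatch is certain: 8 stated, 9 by the stated breakdown, 6 on the form, with one positive item described and none printed. The absence of a scoring rule is equally clear from the available text. The form as printed gives 12 answers and a raw range of 0-72.

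The both-eyes wording is also certain. That it may dilute a difference is plausible, but neither demonstrated nor measurable from the documents. The power figures above mark a range under assumptions and should not be quoted as the trial's loss of power.

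This is a minor point. It is worth acting on because it concerns a primary tolerability variable in a trial that reads no difference as success, and because the eye that was meant cannot be established after data collection.

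**What to change.** 1. **Reconcile section 6.4.3.3 with annex 13.1.** State the number of items on the form actually used and that no item is reversed. For the annexed form this is six two-part items, each part answered 0 to 6.
2. **Fix one scoring rule, valid for that form, before unblinding.** Either supply the Rasch conversion for this form, or use the raw sum of the 12 answers and report it as a 0-72 score. A conversion made for a version with a different number of items should not be assumed to apply. Give the chosen range in Table 4.
3. **Add one instruction line at the baseline and final visits,** identical in both arms, asking the subject to answer for the right (treated) eye. Section 6.4.4 also lists the index at the screening visit; if the form is given then, use the same line. It must be in place before the first form is completed.

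The cost is a few lines of protocol text and one line on the form, with no extra subjects, visits or procedures. The downside is a small departure from the form's both-eyes wording: the items would still say eyes while the instruction names one. That departure is equal in both arms.

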#### 6.4.3.4 Eye surface integrity: conjunctival hyperemia and chemosis

This will be done by means of biomicroscopy using the slit lamp of the research center. A full assessment of the previous segment will be made, which will be recorded in the clinical file. The lighting techniques used will be at the discretion of the IP.

The variables that will be registered in this protocol are:

# Conjunctival hyperemia.

It is defined as the simplest reaction of the conjunctiva to a stimulus, a red appearance secondary to the vasodilation of the conjunctival vessels of variable intensity. He will graduate using the Efron scale. [44] See annex 13.2 Efron scale for conjunctival hyperemia

- Chemosis.
- It is defined as conjunctival edema, the result of an inflammatory reaction. It is qualified as present or absent. The evaluator will use a narrow beam of light at 60 ° and will measure if the conjunctiva separates from the sclera at ≥ 1/3 of the total palpebral opening or if it exceeds the gray line. [43]

#### 6.4.3.4.1 Stains

Staining with green lysine and fluorescein

A drop of topical anesthetic will be instilled in the conjunctival cul-de-sac, then a second drop will be applied to the tip of the strip of green lysine and fluorescein and it will be allowed to slip towards the bottom of the sac. It is essential to quickly evaluate the staining, in sequence, first in the DO and then the OS, so that the observed patterns are equally bright. [19] See Annex 13.3 Oxford Scale

The value obtained according to the Oxford scale will be registered in the CRF.

#### 6.4.3.5 Presence of adverse events

The management of the EAs will be done according to what is described in section 9.3 Adverse events. The PI will register in the corresponding section of the CRF the EA that the subjects of the study will present, as well as referring it in their essential document.

# 6.4.3.6 Intraocular pressure

Tonometry is the objective measure of IOP, based primarily on the force required to flatten the cornea or the degree of corneal indentation produced by a fixed force. Goldman's tonometry is based on the Imbert-Fick principle. [38] The tonometry will be performed, after instillation of a drop of topical anesthetic (tetracaine 0.5%), with fluorescein and the use of the cobalt blue filter (after evaluation of the corneal surface staining). Three shots will be taken, which will be registered in the clinical file and the average will be registered in the CRF.

#### 6.4.3.7 posterior segment

The evaluation of the posterior segment will be carried out under medication mydriasis (tropicamide 0.8% / phenylephrine 5%), in the slit lamp with an aerial loupe (at the choice of the PI). An integral assessment of the fundus (including optic disk, posterior pole and periphery) will be performed in

search of abnormalities that alter the study result. The result of the assessment will be recorded in the clinical file. In the CRF the assessment of the macula and optic nerve as normal, abnormal or abnormality that does not affect will be registered.

#### 6.4.3.8 Vital signs

The vital signs to be evaluated (FC, FR and TAS) can be measured by an assistant duly indicated in the organization of the center and the delegation of responsibilities, the technique to be used for the FC and FR will be with the count of repetitions in one minute by Direct auscultation with stethoscope.

The SBP should be measured with 5 minutes of previous rest, in the left arm. The instrument can be manual or automatic according to the IP. It is necessary that all measurements are equal in circumstances. 3 measurements will be made, with a minimum interval of 5 minutes between them. The IP will record the average in the note and the CRF.

#### 6.4.3.9 Ocular symptomatology

The subject will be questioned directly about the presence in general (since the last visit) of the following symptoms: burning, foreign body sensation and pruritus. Respond about the severity and frequency of symptoms such as:

Severity: Absent (0), very mild (1), mild (2), moderate (3) and severe (4)

Frequency: At all times (4), almost at all times (3), 50% of the time (2), almost at no time (1), at any time (0).

The number corresponding to each symptom will be registered in the CRF.

Post-application symptomology:

The subject will be requested, that in the subject's daily instrument, after registering the application of the product under investigation, mark YES or NO according to the presence of the following symptoms: burning, sensation of a foreign body, red eye and pruritus

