## 6.4.3.2 Goblet cell density (Cytology per impression)

The density of goblet cells in the conjunctiva can be a reflection of the severity of alteration in the ocular surface. [39] It has been determined that the normal density is greater than 500 cel / mm2. [40] Impression cytology refers to the application of a cellulose acetate filter to the ocular surface to remove the superficial layers of the epithelium; these removed cells can be subjected to histological, immunohistological or molecular analysis. [41]

The cytology per impression of the conjunctiva will be done by the researcher using the device provided by the sponsor for this purpose, which may consist of a circular cell of approximately 10 mm in diameter, with a cellulose acetate filter millicell. After ocular surface anesthesia, with topical tetracaine, the researcher will ask the subject to expose the temporal surface of the eye to be evaluated and gently press the cell on the temporal conjunctiva (2 to 3 mm of the sclerocorneal limbus) for 5 seconds and remove the cell with a peeling technique (Illustration 1. Cytology per impression). Immediately fix with diethyl ether spray with one or two shots at 15 cm distance. The investigator will contact the Courier, within the first 24 hours, after the appointment designated by the sponsor for the shipment of the samples to histopathological analysis. You must complete the

requisition form provided by the investigator and attach it to the mailing. The format will consist of three sheets (1 original and 2 copies) which will be assigned as follows: original sheet for the Courier, 1 copy will be collected by the monitor and 1 copy will remain in the research center and will be filed in the corresponding folder to each research subject.

Illustration 1. Cytology per impression

The data of the histopathological report to be recorded in the CRF are: density of goblet cells and degree of squamous metaplasia according to the Nelson scale. (**See Table 5**)

In the visits required to perform this procedure, it will be done prior to the use of ocular surface stains.

Table 5. Nelson classification

Grade	Detail description of the epithelial cells	Characteristics of goblet cells
0	Small and round cells; Large nuclei, 1: 2 ratio with nuclear cytoplasm	Abundant goblet cells (> 500 cells / mm2), globose and oval with an intense PAS-positive staining of the cytoplasm.

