#### **Scrutiny Visit**

Some of these measurements should be complemented with those of the baseline visit and thus meet the eligibility criteria (see Schedule and study diagram), at the discretion of the PI.

- 1. Signature of informed consent.
- 2. General and ophthalmological clinical history.
- 3. Laboratory sample taking.
- 4. Pregnancy test.
- 5. Review of selection criteria
- 6. Visual ability
- 7. Density of goblet cells (Cytology per impression)
- 8. Intraocular pressure.
- 9. Eye comfort index
- 10. Evaluation of ocular signs and symptoms
- 11. Integrity of ocular surface
- a. Epithelial defects (TF and TVL)
- b. TRL
- 12. Subsequent segment evaluation.
- 13. Vital signs

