## 6.5 Timeline and study diagram

Procedures	scrutiny	Basal visit	Visit 1	Final visit	Call Security
Procedures		Day 0	Day 3 ± 1	Day 11 ± 1	Day 13 ± 1
CI signature	Х				
clinic history	Χ				
Ophthalmological clinical history	Х				
Laboratory sample taking	Χ			Χ	
Laboratory tests review		Х			Х
Pregnancy test	Χ			Χ	
Eligibility criteria	Х	Xa			
Assignment		Χ			
Delivery of intervention		Х	Х		
Return of intervention			Χ	Χ	
Adherence evaluation			Х	Х	
Adverse events			Х	Χ	Χ
Intraocular pressure	Х	X 	Х	Х	
Visual ability	Χ	X 	Χ	Χ	
TRL	Х	X 	Х	Х	
Epithelial defects (TF and TVL)	Χ	X 	Х	Χ	
Eye signs and symptoms	Х	X 	Х	Х	
Posterior Segment	Χ	X 		Χ	
Vital signs	Х	X 	Х	Х	
Ocular Comfort Index		Х		Х	
Goblet cell density (cytology by impression)		Х		Х	
Daily delivery of the subject		Χ	Х		
Return / Evaluation of the subject's Journal			Х	Х	
Delivery Quality Questionnaire		Χ			
Return and Evaluation of the quality questionnaire				Х	
Continuity evaluation of the subject		Х	X	X	

a The eligibility criteria will be completed with the revision of the laboratory exams. 1 These measurements may be taken from the result of the screening visit, if it does not exceed the previous 7 days. It is the prerogative of the PI to decide whether to repeat the measurements at the baseline visit.

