#### 6.5.1.2 Basal visit

- Review of laboratory tests: refers to the review and analysis by the IP of the results of the BH, QS and PFH. See 6.4.3.12 Laboratory tests.
- Eligibility criteria: with the laboratory results, the subject's profile will be finalized for inclusion or not.
- Assignment: It refers to determining the intervention that the patient will follow during the study. It will be done according to section 7. Methods. Assignment of the intervention. This assignment will be made at the baseline visit (day 0) and will go along with the indication to start the treatment period the next day (day 1).
- Delivery of intervention: Refers to the delivery of the product under investigation to the patient of the study, by the research center. It will be done according to sections 6.3.1 Managed treatments and 6.3.4.1 Delivery and reception.
- Evaluation of variables: The data of the evaluation of the variables listed below can be taken from the scrutiny visit, as long as it does not exceed 7 days prior to this visit. It is the IP's prerogative to decide whether to use the information from the screening visit or to repeat the evaluations on this visit.
  - o Intraocular pressure
  - o Visual capacity
  - o TRL
  - o Epithelial defects (TF and TVL)
  - o Eye signs and symptoms
  - o Subsequent segment
  - o vital signs

- Eye comfort index: see 6.4.3.3 Eye comfort index
- Density of goblet cells (cytology per impression): see 6.4.3.2 Density of goblet cells (cytology per impression)
- Delivery of the subject's diary: It refers to the delivery by the IP to the subject, the subject's daily instrument.
- Delivery of quality questionnaire: It refers to the delivery by the IP to the subject, the quality questionnaire instrument.

#### 6.5.1.3 Visit 1

- Intervention delivery: see 6.5.1.2 Baseline visit
- Return of intervention: refers to the return of research products to the center by the research subject.
- Evaluation of adherence: refers to the assessment made by the IP according to section 6.3.2.1 Procedure to monitor adherence
- Adverse events: see 6.4.3.5 Presence of adverse events
- Intraocular pressure: see 6.4.3.6 Intraocular pressure
- Visual ability: see 6.4.3.1 Visual capacity
- TRL: see 6.4.3.10 Rupture time of the tear film
- Epithelial defects (TF and TVL): see 6.4.3.4.1 Stains
- Eye signs and symptoms: see 6.4.3.4 Eye surface integrity: and 6.4.3.9 Ocular symptomatology

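### The Visit 1 symptom interview looks back over a pre-dose day that follows impression cytology, which inflates the absolute figures and dilutes any difference between arms

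*Combined protocol and SAP*

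**What the plan says.** Section 6.4.1.2, "Primary outcome variables of tolerability", lists burning, foreign body sensation and itching together with the eye comfort index. Section 6.4.3.9 defines how the three symptoms are scored at visits: "The subject will be questioned directly about the presence in general (since the last visit) of the following symptoms". Severity and frequency are each graded 0 to 4. The same section adds a diary in which the subject marks yes or no for each symptom after each application.

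Section 6.5.1.2 makes the assignment at baseline, day 0, and says that it "will go along with the indication to start the treatment period the next day (day 1"). The schedule in section 6.5 marks "Goblet cell density (cytology by impression") at the baseline and final visits only. Unlike most other eye measurements, it carries no footnote that lets the screening value stand in. Section 6.4.3.2 describes the procedure: "After ocular surface anesthesia, with topical tetracaine", the investigator presses a filter on the temporal conjunctiva for 5 seconds and must "remove the cell with a peeling technique".

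Section 6.4.4 does not fit this schedule: its screening list also includes "Density of goblet cells (Cytology per impression").

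Section 8.3.1 plans tests within and between groups. It calls the product safe and tolerable when no primary variable differs clinically and statistically from the comparator.

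**The concern.** The Visit 1 window opens with a procedure that strips surface cells from the conjunctiva, and closes after one to three days of dosing. Nothing tells the evaluator to leave out the pre-dose day or to record procedure symptoms separately. A subject whose eye burned on the evening of day 0 and not afterwards would answer yes, and the score carries no date by which this could be separated later.

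Two results are exposed. The first is the description of PRO-167 on its own: the Visit 1 symptom frequencies and any change from baseline. Baseline symptoms may be carried over from screening up to 7 days earlier, and in that case the change to Visit 1 would contain the effect of the day 0 cytology. The second is the comparison between gels. A shared background of symptoms makes a true difference harder to see, and the decision rule treats an undetected difference as success.

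**Working it through.** The plan states no figure on this point, so there is none to reproduce. The check has two parts.

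**1. Share of the recall window before dosing**

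Inputs: cytology and baseline on day 0 (sections 6.5 and 6.5.1.2), first application on day 1 (6.5.1.2), Visit 1 on day 3 ± 1 (6.5).

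Pre-dose share of elapsed time = (day 1 − day 0) / (Visit 1 day − day 0):

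- Visit 1 on day 2: 1/2 = 50%
- Visit 1 on day 3: 1/3 = 33%
- Visit 1 on day 4: 1/4 = 25%

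**2. Effect on recorded rates and on the planned test**

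Inputs from the plan: 12 subjects per arm (6.6), Pearson chi-square on 2x2 tables at alpha 0.05 (8.3.1).

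Assumptions: the documents give neither the gel symptom rates p nor the rate q of symptoms from the procedure. I take q as equal in both arms and independent of gel symptoms, and reduce the outcome to any symptom or none. The plan states no cut-point for the 0 to 4 scores.

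Recorded rate = 1 − (1 − q)(1 − p).

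*Equal gels, p = 10% in both arms.* At q = 20% each arm is recorded at 1 − 0.8 × 0.9 = 28%. At q = 50% it is 1 − 0.5 × 0.9 = 55%. The difference between arms stays at 0 for every q. The test rejects in 1.5% of trials at q = 0, 4.7% at 20%, 5.7% at 30% and 6.3% at 50%. These rejections split evenly between the two directions, so nothing accumulates against PRO-167.

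*Gels that differ, p = 10% v 40%.* The recorded difference is (1 − q) × 30 points. Power is by exact enumeration of the uncorrected Pearson test:

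| q | Recorded rates | Difference | Power |
|---|---|---|---|
| 0% | 10% v 40% | 30 points | 39% |
| 5% | 14.5% v 43% | 28.5 points | 34% |
| 10% | 19% v 46% | 27 points | 30% |
| 20% | 28% v 52% | 24 points | 25% |
| 30% | 37% v 58% | 21 points | 21% |
| 50% | 55% v 70% | 15 points | 13% |

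A larger contrast of 10% v 50% follows the same pattern: power is 60% at q = 0, 40% at 20%, 32% at 30% and 19% at 50%.

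**The case against.** A reader might infer that procedure irritation is scored as intolerance to PRO-167 and counts against it. The documents do not support that. Allocation is 1:1, the trial is double blind, both arms have identical procedures, and section 8.3.1 judges the product against its comparator. An equal background adds no systematic difference, as the equal-gel case shows. This objection stands in full.

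The protocol also has a dose-linked record. The diary is completed after each application and covers all three symptoms, so the trial as a whole can tell product from procedure to some degree. This stands in part: the diary gives only yes or no, without the severity and frequency grades, and nothing makes it the primary measure in place of the interview.

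Visit 1 is not named as the primary time point. The final interview looks back only to Visit 1, a window that holds most of the treatment period and no baseline cytology. The eye comfort index asks about the past week and is scheduled at baseline and the final visit, so its final score does not reach back to day 0. This confines the problem to one interview. It does not remove it, because no other time point is named as primary and section 6.4.4 has the primary variables measured and evaluated at each visit.

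The remaining objections concern size. No rate of procedure symptoms is given, a low rate costs little power, and brief irritation might be graded as hardly ever present. Even without contamination, power for 10% v 40% is only 39%, so 12 per arm is the larger limit. All of this is fair. Finally, if cytology were done only at screening, as one reading of section 6.4.4 allows, the problem would shrink.

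**Conclusion.** The point holds for the Visit 1 interview. As scheduled, the recall window for three primary tolerability symptoms includes a pre-dose day after impression cytology under tetracaine, amounting to 25% to 50% of the elapsed time. The consequence is inflated absolute and within-arm symptom figures for both gels, and a between-arm contrast shrunk by the factor 1 − q. The shrinkage favours a finding of no difference, which is the finding that the plan rewards.

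The direction follows from the schedule if cytology or its anaesthetic causes any symptoms. The size does not: the power figures rest on assumed gel and procedure rates and an any-or-none outcome, and range from a small loss (39% to 34% at q = 5%) to a large one (13% at q = 50%). The conclusion also assumes that cytology takes place at baseline, as sections 6.5 and 6.5.1.2 have it. It is worth correcting because the change is nearly free and the information cannot be recovered once the undated score is recorded.

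**What to change.** In section 6.4.3.9 and the CRF, word the Visit 1 question so that it covers the time since the first application (day 1). The wording can stay as it is for the final visit: the stains and anaesthetic used at Visit 1 remain in that window, but no cytology does.

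Reconcile section 6.4.4, which lists cytology at screening, with sections 6.5 and 6.5.1.2, which place it at baseline.

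The cost is one phrase in the protocol and CRF plus one consistency correction, with no added visit, procedure or subject. The small downside is that the subject has to leave out the evening of day 0 when answering.
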